16. REGULATORY ETHICS, INFORMED CONSENT, AND SUBJECT PROTECTION

16.1. Regulatory Considerations

According to the corresponding regulatory requirements in China, an application should be submitted to the NMPA before starting a new drug study and the study can only be carried out after approval is obtained. The clinical approval number for SHR-1210 is 2016L01455.

The legal basis for the design of this protocol is as follows:

- 1) Provisions for Drug Registration
- 2) Good Clinical Practice
- 3) Technical Guidelines for Clinical Pharmacokinetic Study of Chemical Drugs
- 4) Consensus on ethical principles based on international ethics guidelines, including the Declaration of Helsinki and the Council for International Organizations of Medical Sciences (CIOMS) International Ethics Guidelines
- 5) ICH Guidelines
- 6) Other applicable laws and regulations

16.2. Ethical Standards

The investigators will ensure that this study is fully implemented in accordance with the requirements for fully protection of the safety and rights of the subjects.

This study protocol must first be reviewed and approved in writing by the EC of the hospital before being implemented. The study protocol, protocol amendments, informed consent form, and other relevant documents such as recruitment advertisements should be submitted to the EC. This clinical study must be conducted in accordance with the Declaration of Helsinki, NMPA's Good Clinical Practice (GCP), and applicable laws and regulations. Before the study is initiated, approval must be obtained from the EC of the hospital.

The study protocol must not be unilaterally modified without approvals from both the sponsor and investigators. The investigators can modify or deviate from the study protocol before obtaining an approval from the EC/IRB only when in purpose of eliminating direct and

immediate harm to the subject. Besides, the deviation or change and the corresponding reason, and the recommended protocol amendment should be submitted to the EC/IRB for review. The investigators must provide explanations and document any protocol deviation.

During the study, any changes to this study protocol must be submitted to the EC. If necessary, corresponding changes should be simultaneously made to other study documents and be submitted and/or approved according to the pertinent requirements of the EC. The investigators are responsible for submitting the interim reports regularly according to the pertinent requirements of the EC. After the end of the study, the completion should be informed to the EC.

16.3. Independent Ethics Committee

The protocol, informed consent form, recruitment material, and all subject materials must be reviewed and approved by the EC. Subjects may be enrolled only after the protocol and informed consent form have been approved. Any revisions to the protocol must be reviewed and approved by the EC prior to being implemented. All revisions to the informed consent form must be approved by the EC.

16.3.1. Informed consent form and other written information for subjects

The informed consent form describes the investigational drug and study process in detail and fully explains the risks of the study to the subjects. Written documentation of informed consent must be obtained before starting any study-related procedures.

16.3.2. Informed consent process and records

Informed consent will begin before an individual decides to participate in the clinical study and continues during the entire clinical study. The risks and potential benefits of participating in the study should be discussed fully and in detail with the subjects or their legally acceptable representatives. Subjects will be asked to read and review the informed consent form that has been approved by the EC. The investigators will explain the clinical study to the subjects and answer any questions posed by the subjects. Subjects can only participate in the study after they have signed the informed consent forms. During the clinical study, subjects can withdraw the informed consents at any time. One copy of the signed informed consent form will be kept by the subjects. Even if a patient refuses to participate in this study, his or her rights will be fully protected, and the nursing quality will not be affected.

16.4. Confidentiality of Subject Information

The confidentiality of subject information will be strictly enforced by the investigators, participated study personnel, and sponsor and its representative. In addition to the clinical information, confidentiality also simultaneously covers biological samples and genetic tests of

the subjects. Therefore, the study protocol, documentation, data, and other information generated from these materials will be kept strictly confidential. All relevant study or data information should not be disclosed to any unauthorized third-party without prior written approval from the sponsor.

Other authorized representatives of the sponsor, IRB or regulatory authorities, and the representatives of the pharmaceutical company that provides the investigational drug can examine all the documents and records that are maintained by the investigators, including but not limited to medical records and subject's administration records. Study sites should allow access to these records.

The contact information of the subjects will be safely kept in each study site and only used internally during the study. When the study is ended, all the records will be kept in a secure place based on the time limit specified by local IRB and regulations.

This should not include the contact information or identification information of subjects. Instead, individual subjects and their study data will be given a unique study identification number. The study data entry and study management system used by the study personnel at study sites should be confidential and password-protected.

16.4.1. Use of samples, specimens, or data

This section should include the following:

- Planned use: The samples and data collected in accordance with the protocol will be used for the detection of biomarkers and will not be used for any unrelated purposes.
- Storage: Samples and data will be numbered for storage in this study. The data in the computer will also be password-protected. Only the study personnel can have access to these samples and data.

17. PUBLICATION OF STUDY RESULTS

The study results belong to Jiangsu Hengrui Pharmaceuticals Co., Ltd. If the investigators plan to publish any research-related data and information, Hengrui should be provided with the manuscript, abstract, or full text of all planned publications (poster, invited lectures, or guest lectures) at least 30 days prior to the submission of documents for publication or other forms of publication.

18. CLINICAL STUDY PROGRESS

Anticipated enrollment of the first subject: Jun. 2017

Anticipated enrollment of the last subject: Nov. 2017

Anticipated study completion: Dec. 2019

APPENDIX I. ECOG PS

Grade	Performance Status
0	Fully active, able to carry on all pre-disease performance without restriction
1	Restricted in physically strenuous activity but ambulatory and able to carry out work of a light or sedentary nature, e.g., light house work, office work.
2	Ambulatory and capable of all self-care but unable to carry out any work activities. Up and about more than 50% of waking hours.
3	Capable of only limited self-care, confined to bed or chair 50% or more of waking hours.
4	Completely disabled; cannot carry on any self-care; totally confined to bed or chair.
5	Death.

APPENDIX II. CREATININE CLEARANCE CALCULATION

Creatinine Clearance Calculation Using the **Cockcroft-Gault** Formula

Serum Creatinine Concentration (mg/dL):

$$\text{Creatinine clearance in males (mL/min)} = \frac{(140 - \text{age}) \times (\text{weight})^a}{72 \times \text{serum creatinine}}$$

$$\text{Creatinine clearance in females (mL/min)} = \frac{0.85 \times (140 - \text{age}) \times (\text{weight})^a}{72 \times \text{serum creatinine}}$$

Serum Creatinine Concentration ($\mu\text{mol/L}$):

$$\text{Creatinine clearance in males (mL/min)} = \frac{(140 - \text{age}) \times (\text{weight})^a}{0.818 \times \text{serum creatinine}}$$

$$\text{Creatinine clearance in females (mL/min)} = \frac{0.85 \times (140 - \text{age}) \times (\text{weight})^a}{0.818 \times \text{serum creatinine}}$$

a Age in years, weight in kg.

APPENDIX III. STAGING OF HODGKIN'S LYMPHOMA

Stage I Single lymph node involvement (I) or local involvement of a single extralymphatic organ or site (I_E).

Stage II Involvement of two or more lymph node regions (II) on the same side of the diaphragm or localized involvement of a single extralymphatic organ or site in association with regional lymph node involvement, with or without involvement of other lymph node regions on the same side of the diaphragm (II_E).

Note: The number of involved lymph node regions can be represented by subscripts (for example, II₃).

Stage III Involvement of lymph node regions above or below the diaphragm (III); involvement of lymph node groups above and below the diaphragm and outside of the lymph nodes in a nearby organ or site (III_E); involvement of lymph node groups above and below the diaphragm and in the spleen (III_S); or involvement of lymph node groups above and below the diaphragm, outside the lymph nodes in a nearby organ or site, and in the spleen (III_{E+S}).

Stage IV Diffuse (multiple sites) involvement of one or more extralymphatic organs with or without related lymph node involvement or involvement of solitary extralymphatic organs with involvement of distant lymph nodes (non-lymphatic areas).

A Absence of systemic symptoms

B Pyrexia of > 38 °C of unknown cause; night sweats; weight loss of > 10% (within 6 months before diagnosis)

APPENDIX IV. INTERNATIONAL PROGNOSTIC SCORE (IPS)

1 point for each of the following factors:

Albumin < 4 g/dL

Hemoglobin < 10.5 g/dL

Male

Age \geq 45 years old

Stage IV lesion

WBC increased (WBC count of at least 15000/mm³)

Lymphocyte decreased (lymphocyte count less than 8% of total WBCs, and/or lymphocyte count less than 600/mm³)

APPENDIX V. RESPONSE EVALUATION CRITERIA

Lugano 2014 Revised Criteria for Response Assessment of Lymphoma		
Response and Site	Metabolic Response (PET-CT)	Radiologic Response (CT)
CR	CMR (complete metabolic response)	CRR (complete radiologic response)
Lymph nodes and extranodal sites	Score 1, 2, or 3 with or without a residual mass on PET 5-point scale. It is recognized that in Waldeyer's ring or extranodal sites with high physiologic uptake or with activation within spleen or marrow (e.g., with chemotherapy or myeloid colony-stimulating factors), uptake may be greater than normal mediastinum and/or liver. In this circumstance, complete metabolic response may be inferred if uptake at sites of initial involvement is no greater than surrounding normal tissue even if the tissue has high physiologic uptake.	Target nodes/nodal masses must regress to ≤ 1.5 cm in LD _i No extranodal sites of disease
Nonmeasured lesions	Not applicable	Absent
Organ enlargement	Not applicable	Regress to normal
New lesions	None	None
Bone marrow	No evidence of FDG-avid disease in marrow	Normal by morphology; if indeterminate, IHC negative
PR	PMR (partial metabolic response)	PRR (partial radiologic response)
Lymph nodes and extranodal sites	Score 4 or 5 with reduced uptake compared with baseline and residual mass(es) of any size. At interim, these findings suggest responding disease At end of treatment, these findings indicate residual disease	$\geq 50\%$ decrease in SPD of up to 6 target measurable nodes and extranodal sites; when a lesion is too small to measure on CT, assign 5 mm \times 5 mm as the default value; when no longer visible, 0 \times 0 mm; for a node > 5 mm \times 5 mm, but smaller than normal, use actual measurement for calculation;
Nonmeasured lesions	Not applicable	Absent/normal, regressed, but no increase
Organ enlargement	Not applicable	Spleen must have regressed by $> 50\%$ in length beyond normal
New lesions	None	None
Bone marrow	Residual uptake higher than uptake in normal marrow but reduced compared with baseline (diffuse uptake compatible with reactive changes from chemotherapy allowed). If there are persistent focal changes in the marrow in the context of a nodal response, consideration should be given to further evaluation with MRI or biopsy or an interval scan.	Not applicable

Lugano 2014 Revised Criteria for Response Assessment of Lymphoma		
Response and Site	Metabolic Response (PET-CT)	Radiologic Response (CT)
SD	No metabolic response	SD
Lymph nodes and extranodal sites	Score 4 or 5 with no significant change in FDG uptake from baseline at interim or end of treatment.	< 50% decrease from baseline in SPD of up to 6 dominant, measurable nodes and extranodal sites; no criteria for progressive disease are met
Nonmeasured lesions	Not applicable	No increase consistent with progression
Organ enlargement	Not applicable	No increase consistent with progression
New lesions	None	None
Bone marrow	No change from baseline	Not applicable
PD	Metabolic progression	Radiologic progression
Individual target nodes/nodal masses and extranodal lesions	Score 4 or 5 with an increase in intensity of uptake from baseline and/or New FDG-avid foci consistent with lymphoma at interim or end-of-treatment assessment.	An individual node/lesion must be abnormal with: $LDi > 1.5$ cm and Increase by $\geq 50\%$ from PPD nadir and An increase in LDi or SDi from nadir 0.5 cm for lesions ≤ 2 cm 1.0 cm for lesions > 2 cm; In the setting of splenomegaly, the splenic length must increase by $> 50\%$ of the extent of its prior increase beyond baseline (e.g., a 15-cm spleen must increase to > 16 cm); if no prior splenomegaly, must increase by at least 2 cm from baseline; New or recurrent splenomegaly.
Nonmeasured lesions	None	New or clear progression of preexisting nonmeasured lesions
New lesions	New FDG-avid foci consistent with lymphoma rather than another etiology (e.g., infection, inflammation). If uncertain regarding etiology of new lesions, biopsy or interval scan may be considered	A new node > 1.5 cm in any axis; a new extranodal site > 1.0 cm in any axis; if < 1.0 cm in any axis, its presence must be unequivocal and must be attributable to lymphoma; Assessable disease of any size unequivocally attributable to lymphoma
Bone marrow	New or recurrent FDG-avid foci	New or recurrent involvement

CR = complete response; PR = partial response; SD = stable disease; PD = progressive disease;

SPD: sum of the product of the perpendicular diameters for multiple lesions; PPD: cross product of the LDi and perpendicular diameter; LDi : longest transverse diameter of a lesion; SDi : shortest axis perpendicular to the LDi

PET 5-Point Scale

Score	PET/CT Examination Result
1	No uptake above background
2	Uptake \leq mediastinum
3	Uptake $>$ mediastinum but \leq liver
4	Uptake moderately $>$ liver
5	Uptake markedly higher than liver and/or new lesions

1. REVISION

Updated to Version 3.0 on 30 Aug. 2020. Formulated with reference to the protocol No. SHR-1210-II-204 (Version 3.0, 19 Jul., 2017).

Content	Before	After
Cover	1. The version number is 2.0 2. The version date is 4 Apr., 2018	1. The version number is 3.0 2. The version date is 30 Aug., 2020
Definition of FAS	
Full Analysis Set (FAS): eligible subjects who have received the investigational drug and meet the following requirements.
 
(1) Subjects who have received rescue autologous stem cell transplant after chemotherapy, and then have recurrence or progression;
 
(2) Subjects who have not received autologous stem cell transplant are required to have received the following treatment:
 
The first-line chemotherapy must be systemic multi-drug combination chemotherapy. For subsequent chemotherapy, it is required that at least one line of chemotherapy is systemic multi-drug combination chemotherapy.
 
Patients with refractory disease are patients who did not achieve PR after ≥ 2 treatment cycles or CR after ≥ 4 treatment cycles, or patients who developed progressive disease, regardless of number of treatment cycles.
 
Patients with relapsed disease are patients who were recently treated with at least second-line chemotherapy prior to recurrence.
	Full Analysis Set (FAS): eligible subjects who have received the investigational drug.
5.1.4 Covariates and subgroups	Subjects who received the highest number of lines of prior chemotherapy or autologous stem cell transplant but achieved non-CR/non-PR are classified as subjects with refractory diseases, and others are classified as subjects with relapsed diseases.	
Relapsed: Best overall response to the last chemotherapy/transplant is CR or PR, and time from the end of chemotherapy/transplant to progression is > 6 months.
 
Refractory: 1. Best overall response to the last chemotherapy/transplant is CR, PR, or not evaluated, and time from the end of chemotherapy/transplant to progression is ≤ 6 months. Or, 2. Best overall response to the last chemotherapy/transplant is PD or SD.
 
Missing: Response to the last chemotherapy/transplant is not evaluated, and time from the end of last chemotherapy/transplant to progression is > 6 months.

2. INTRODUCTION

This study is a phase II clinical study evaluating the efficacy and safety of SHR-1210 in the treatment of patients with refractory or relapsed classic Hodgkin's lymphoma.

2.1. Study Design

This study adopts a multi-center, open-label, single-arm design to evaluate the efficacy and safety of SHR-1210 in patients with relapsed or refractory classic Hodgkin's lymphoma and the PK parameters of 12 subjects at the same time. Sixty subjects who meet the eligibility criteria will be enrolled and given SHR-1210 at 200 mg/dose on day 1 of each 2-week cycle, until the following condition occurs: progressive disease (PD), intolerable toxicity, or other reasons specified in the protocol. After treatment, the subjects entered the follow-up period would receive safety follow-up or survival follow-up.

2.2. Study Objectives

2.2.1. Primary objective

To evaluate the efficacy, namely objective response rate (ORR), of PD-1 antibody SHR-1210 in the treatment of relapsed or refractory classic Hodgkin's lymphoma.

2.2.2. Secondary objectives

- To observe and evaluate the duration of response (DoR), progression-free survival (PFS), time to response (TTR), and overall survival (OS) of PD-1 antibody SHR-1210 in the treatment of patients with relapsed or refractory classic Hodgkin's lymphoma (cHL).
- To evaluate the safety of PD-1 antibody SHR-1210 in patients with relapsed or refractory classic Hodgkin's lymphoma (cHL).

2.3. Sample Size

This study adopts a single-arm design. The primary objective is to evaluate the efficacy of SHR-1210 in the treatment of relapsed or refractory cHL. The study endpoint is ORR. Based on historical research data and research results of similar products, combined with current clinical practice requirements, only when the lower limit of the 95% confidence interval for ORR obtained from the study is greater than 40%, it can be considered as effective. Therefore, the sample size for this study is determined based on the following 2 points: 1. the exact method (Clopper-Pearson) is used to calculate the 95% confidence interval for ORR; 2. the lower limit of the confidence interval is greater than 40%. Assume that the ORR of SHR-1210 in the treatment of relapsed or refractory cHL reaches 65%, a power of 92.90% can be obtained with 50 subjects. Combined with a dropout rate of 20%, this study intends to enroll 60 subjects.

3. STATISTICAL HYPOTHESES

Hypotheses of ORR are as follows:

$$H_0: \text{ ORR} = 40\%$$

$$H_a: \text{ ORR} \neq 40\%$$

$$\alpha = 0.05 \text{ (two-sided)}$$

4. STUDY ENDPOINTS

4.1. Efficacy Endpoints

Primary efficacy endpoint:

Objective response rate (ORR) assessed by the independent review committee (IRC), including the proportion of complete response (CR) and partial response (PR).

Secondary efficacy endpoints:

- Objective response rate (ORR) assessed by the investigators, including the proportion of complete response (CR) and partial response (PR)
- Duration of response (DoR)
- Progression-free survival (PFS): The date of first PD documented after CR, PR, or SD is used as the date of progression; if the subject does not achieve CR, PR, or SD following PD, then the date of initial PD is used as the date of progression.
- Time to response (TTR)
- Overall survival (OS)
- Time to progression (TTP)

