- [9] Coagulation function: When international normalized ratio (INR) is not available, prothrombin time (PT) will be used. Measure once every 2 cycles during treatment
- [10] Thyroid function: including TSH, FT3, and FT4. Measure once every 4 cycles during treatment
- [11] Virological examination: including HIV-Ab, HBV, and HCV infection testing. HBV testing requirements: HbsAg (qualitative), HbsAb (qualitative), HbcAb (qualitative), HbeAg (qualitative), and HbeAb (qualitative) should be tested at screening. If HBV infection is suspected, HBV-DNA should be tested (qualitatively; if positive, then quantitatively). HCV testing requirements: HCV-Ab is tested at screening to determine the presence of HCV infection. If positive, HCV-RNA will be tested (qualitatively; if positive, then quantitatively). For patients with hepatitis virus infection during the screening period, virological examination will be performed every 2 cycles during the treatment period, and the examination will be performed at the end of the treatment and during the safety follow-up; for patients with HBV infection, they will be tested for HBV-DNA (quantitative), and for patients with HCV infection, they will be tested for HCV-RNA (quantitative).
- [12] Blood HCG test: Only for women of child bearing potential (WOCBP); test within 7 days before the first dose, and at least once every 4 weeks (± 7 days) thereafter, regardless of the dosing cycle.
- [13] Echocardiography: Perform according to local standard practice when clinically indicated.
- [14] Tumor CT or MRI examination: Evaluate according to IWG2014 criteria, including CT scans with contrast of the chest, abdomen, pelvis, and any other sites of known lesions (such as neck). If the subject is allergic to contrast media or has bronchial asthma, kidney damage, or other diseases that make it difficult to perform contrast imaging, the subject can undergo chest CT without contrast + MRI scans of abdomen, pelvis, and any other sites of known lesions (such as neck). Evaluation will be carried out on D1 (± 7 days) of Weeks 9, 17, 25, 37, and 49 after the start of treatment, then every 16 weeks (± 14 days) until Week 97, and then every 26 weeks (± 21 days) until PD (for subjects who continue to receive the study treatment after radiographic progression, evaluation will be carried out until the investigational drug is discontinued), start of new anti-tumor treatment, or death.

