4. STUDY DESIGN

This study adopts an open-label, single-arm, and multi-center design to evaluate the efficacy and safety of SHR-1210 in patients with relapsed or refractory classic Hodgkin's lymphoma, and to evaluate the PK parameters of 12 subjects at the same time. Sixty subjects who meet the enrollment conditions will be enrolled and given SHR-1210 at 200 mg/dose on D1 of each 2-week cycle, until the following conditions occur: progressive disease (PD), intolerable toxicity, or other reasons specified in the protocol. After treatment, the subjects will enter the follow-up period to receive safety follow-up or survival follow-up.

SHR-1210 is an immune checkpoint inhibitor. According to the experience with similar drugs, some subjects may experience delayed or early pseudo progression after receiving the immunotherapy agents. Therefore, subjects with first PD are allowed to continue to receive treatment under the premise of no obvious clinical deterioration per the judgment of the condition by the investigators, until PD is still determined in the next imaging evaluation.

The diagram of study design is shown as follows:

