8.6. Criteria for Continuing Treatment Beyond Progression

Some subjects receiving immunotherapy can still benefit clinically after radiographic progression. The study treatment may be continued after PD defined per Lugano 2014 criteria for subjects who meet the criteria below:

- The investigators deem that it is in the best interest of the subject to continue treatment, and subject is not required to start other anti-tumor treatment immediately;
- The subject is able to tolerate continued study treatment
- No significant deterioration in subject's performance status, and no significant worsening of cancer-related symptoms
- Before continuing the study treatment, it must be reviewed and approved by the medical monitor

If it is decided that the subject will continue the study treatment after progression, the subject should continue to be treated, evaluated, and followed up according to the protocol requirements.

Subjects should withdraw from study treatment if further progression is observed at the next assessment. The initial date of investigator-assessed progression should be used for all statistics analyses involving progression, regardless of whether the subject continues the study treatment beyond progression.

If the subject discontinues treatment due to deterioration of the general condition without objective evidence for PD, the progression will be reported as "general deterioration". More objective evidences (such as imaging confirmation) of progression of these subjects should be obtained after treatment discontinuation.

For subjects who withdraw from the study due to intolerable toxicity without radiographic PD observed, the imaging examination should be performed at the same frequency, until PD or start of other anti-tumor treatment. The radiographic evidence of PD of these subjects must be obtained whenever possible.

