9. ASSESSMENTS

9.1. Assessment of Efficacy

The Lugano 2014 criteria are used to evaluate the objective response rate (ORR), including the CR and PR cases.

ORR: Defined as the proportion of subjects whose best response reaches CR or PR from the first dose to the occurrence of PD or the start of new anti-tumor treatment, whichever comes first

PFS: Defined as the time from the date of the first dose to the first documented PD or all-cause death, whichever occurs first. If the subject has not had PD or died by the data cut-off date, the cut-off date is the date of the subject's last efficacy evaluation. If the subject has not received tumor evaluation, the cut-off date is the date of the first dose, and PFS lasts for 1 day.

DoR: Defined as the time from the date of the first CR or PR to the date of initial assessment of PD or all-cause death, whichever comes first. If the subject has not had PD or died by the data cut-off date, the censoring date is the date of the subject's last efficacy evaluation. Only applicable to subjects with CR/PR.

TTR: Defined as the time from D1 of administration to the first evaluation of PR or CR, whichever comes first. Only applicable to subjects with CR/PR.

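### When a first post-baseline PD is followed by CR, PR or SD and then PD, SAP 4.1 dates PFS progression at the later PD, against the protocol's first-PD rule

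*SAP*

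**What the plan says.** SAP 4.1 gives PFS a dating rule in two clauses. The first is "The date of first PD documented after CR, PR, or SD is used as the date of progression". The second is the fallback: "if the subject does not achieve CR, PR, or SD following PD, then the date of initial PD is used".

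Protocol 9.1 defines PFS as "the time from the date of the first dose to the first documented PD or all-cause death", whichever occurs first, and does not limit this to one assessor. Protocol 8.6, on treatment beyond progression, adds: "The initial date of investigator-assessed progression should be used for all statistics analyses involving progression". It applies this whether or not the subject stays on treatment.

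Assessments after a first PD are foreseen. Protocol section 4 says "subjects with first PD are allowed to continue to receive treatment under the premise of no obvious clinical deterioration". Note 14 to the Schedule of Activities provides for scans in these subjects: "for subjects who continue to receive the study treatment after radiographic progression, evaluation will be carried out until the investigational drug is discontinued".

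SAP Appendix 1.1 row 4 makes progression an event on the date of progressive disease, without saying which PD is meant if there are two. SAP 5.4 runs the secondary efficacy analyses on both the IRC and the investigator results. SAP section 1 states that the SAP was written against protocol Version 3.0, which contains the first-PD rule. Protocol 12.2 lets the SAP revise protocol content, but asks that a changed endpoint definition be reflected in a protocol amendment.

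**The concern.** Treatment may continue past a first PD because pseudo-progression is expected in some subjects. The sequence PD, then disease control, then PD is therefore one that the trial itself foresees. For that sequence the two documents give different event dates from identical scans. The protocol settles the matter for exactly this setting by keeping the initial date, and the SAP sets that date aside.

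At stake is the meaning of the reported PFS. A reader who relies on the protocol definition would take it as time to first progression, while for these subjects the programmed endpoint would be time to a later one. Two analysts, each following one document faithfully, could report different PFS times.

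**Working it through.** The documents state no figure that depends on this rule, so there is none to reproduce. The check applies each rule literally to sequences of assessments at the scheduled weeks.

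**Inputs**
- Scan schedule: day 1 of Weeks 9, 17, 25 and 37, each ±7 days (Protocol 8.2 and Schedule of Activities note 14).
- Study day: the day of first dose is day 1 (SAP 5.1.2), so day = 7 × (week − 1) + 1.
- Months: days / 30.44. SAP 5.1.3 uses this divisor for its other durations; using it for PFS is an assumption.
- No missed scans, new anti-tumour treatment or death, so no Appendix 1.1 censoring row intervenes.

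**Scheduled dates**
- Week 9: 7 × 8 + 1 = day 57; 57 / 30.44 = 1.87 months
- Week 17: 7 × 16 + 1 = day 113; 113 / 30.44 = 3.71 months
- Week 25: 7 × 24 + 1 = day 169; 169 / 30.44 = 5.55 months
- Week 37: 7 × 36 + 1 = day 253; 253 / 30.44 = 8.31 months

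**Rules applied**

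| Assessments from Week 9 on | Protocol 9.1 | SAP 4.1, first clause | SAP 4.1, fallback | Result |
|---|---|---|---|---|
| PD, SD, PD | day 57 | day 169 | not met | conflict |
| SD, PD, SD, PD | day 113 | day 113 read literally; day 253 if the fallback is taken to discard the first PD | not met | ambiguous |
| PD, SD, SD | day 57 | no date | not met | 4.1 silent; Appendix 1.1 row 4 points to day 57 |
| SD, PD | day 113 | day 113 | day 113 | agree |
| PD, PD | day 57 | no date | day 57 | agree |
| PR, PD, PD | day 113 | day 113 | day 113 | agree |

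**Size in the conflicting sequence**
- Nominal dates: 169 − 57 = 112 days; 112 / 30.44 = 3.68 months. PFS is 1.9 months under the protocol and 5.6 under the SAP.
- Shortest gap within the windows (first scan 7 days late, last scan 7 days early): 112 − 14 = 98 days; 98 / 30.44 = 3.22 months.
- Longest gap (first scan early, last scan late): 112 + 14 = 126 days; 126 / 30.44 = 4.14 months.
- If disease control lasts until Week 37, the SAP date is day 253 (8.3 months), against day 57 under the protocol.

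**The case against.** The strongest reply is that the affected group is narrow and the endpoint descriptive. Under Protocol 8.6, treatment beyond progression requires several conditions and the medical monitor's approval, and it ends if further progression is seen at the next assessment. PFS is secondary and carries no test. This stands, and it limits the importance of the point. It does not remove the conflict.

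It might also be said that the SAP rule is a deliberate way of handling pseudo-progression. But the protocol's allowance for pseudo-progression concerns treatment. Where Protocol 8.6 turns to analysis dates, it keeps the initial one. That section names investigator-assessed progression only; for IRC-based PFS the conflict is with Protocol 9.1.

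A reader might infer more than the documents support:

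- **That the SAP leaves two further sequences undefined.** For PD then SD with no later PD, SAP 4.1 gives no date. However, there is only one PD, and Appendix 1.1 row 4 points to an event on it. For SD, PD, SD, PD, the first clause read literally agrees with the protocol. The doubt arises only from reading the fallback in reverse, so this is a drafting ambiguity and not a shown conflict.
- **That DoR or ORR is also contradicted.** The protocol counts as responders subjects "whose best response reaches CR or PR from the first dose to the occurrence of PD or the start of new anti-tumor treatment". A subject whose first assessment is PD is not one, so DoR, defined as "the time from the date of the first CR or PR to the date of initial assessment of PD or all-cause death" and applicable only to responders, does not arise. Comparing the ORR window with SAP PFS restates the same conflict.
- **That disagreement between IRC and site makes the pattern common.** The documents do not say whose assessment governs further scans, and the IRC Charter is not among them.
- **That the rule must lengthen median PFS.** It delays the affected subject's own date. Its effect on the Kaplan-Meier median may be nil, and need not run one way when others are censored between the two dates.

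**Conclusion.** The conflict is real for one sequence: first post-baseline assessment PD, then CR, PR or SD, then PD. SAP 4.1 takes the later PD; Protocol 9.1 takes the first, and Protocol 8.6 requires the initial date for investigator-assessed progression. Nothing in Appendix 1.1 resolves it, and no protocol amendment adopting the SAP rule is seen in the supplied documents. In the Week 9 / Week 25 example, that subject's PFS is 112 days longer under the SAP (98 to 126 with the windows). This rests on the scheduled dates, a 30.44-day month and no intervening censoring.

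The number of such subjects is not given, so no effect on the median can be stated. The ORR decision rule is unaffected. The point should be fixed, because the endpoint as programmed would not be the endpoint as defined, but it does not threaten the trial's main conclusion.

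**What to change.** Replace the PFS sentence in SAP 4.1 with the protocol's rule, for example: *PFS ends at the first documented PD or at death from any cause, whichever is earlier, regardless of later assessments or continued treatment. The rule is applied separately to the investigator and IRC reads and is subject to the censoring rules in Appendix 1.1.*

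In Appendix 1.1 row 4, change the date entry to *date of first documented progressive disease*. Together these two edits also settle the ambiguous SD, PD, SD, PD sequence and the sequence on which SAP 4.1 is silent.

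If the later date is what the sponsor intends, the protocol should be amended to say so, as Protocol 12.2 asks for a changed endpoint definition.

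The SAP route costs one sentence, one table entry and a small programming change. It needs no new data.
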